**Statistical Analysis Plan:**

The primary analysis of the primary endpoint will be a comparison of the primary clinical functional patency by treatment approach, where the distributions are based on available follow up to 12 months. A log-rank test will be used to evaluate the null. The secondary analytic method of the secondary endpoints will utilize a Cox regression model to adjust for the subject factors to adjust for baseline imbalance such as vein size. Based on a recent publication utilizing primary patency rate as the main outcome, the reported rates of primary functional patency of one-stage BBAVF was 56% at 12-month follow-up and was 72% for the two-stage procedure.[12] Based on a two-sided Fisher's exact test at significance level of 5%, a sample size of 153 per group is required to achieve a power of 80% to detect the percentage patency difference of 16% (56% vs. 72%). A sample size of 336 participants (168 per arm), with an estimated loss to follow-up rate of 10%, will be required to achieve a 5% significance level. With the restraint of the time and resources of this ASDIN research grant, the pilot trial will be exploratory and will be used to demonstrate the feasibility of the research plan in a high-risk ESRD population and the recruitment target.

The changes in the individuals' PROMIS domain scores and overall scores from the baseline will be compared between the patients who underwent a one-stage procedure and those who had a two-stage procedure. The analysis will be performed after excluding those who do not complete the two-stage procedure (only first procedure for two-stage approach). The impact of clinical events including infection and catheter-related complication on PROMIS domain scores will be evaluated using the student T-test.

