### Design:

A BBAVF is a reliable autogenous hemodialysis access in patients without suitable cephalic vein.[1, 2] It can be created in either one or two stages.[3] The advantage of the one-stage approach is a shorter time between access creation and the cannulation for HD. The disadvantage is the potential for a longer upper arm incision if the AVF fails to mature. Although the two-stage approach can circumvent a more extensive procedure if the AVF fails, the need for two separate operations usually leads to more extended CVC dependency and a higher risk of CVC-related bacteremia (CRB). While literature confirms good results for BBAVFs, comparative studies of one-stage and two-stage methods are limited.[1] They rest on small case series and few have reported relevant clinical outcomes, including functional patency, duration of CVC dependency, and postoperative complications. In addition, an insufficient number of studies have used intention-to-treat analysis to account for the risk of primary fistula failure. The majority of these studies have concentrated on the fistula-related outcomes rather than patient centric and patient-reported outcomes (PROs), including the quality of life (QOL) measure.[3] There is a clinical equipoise in the surgical approach for the creation of a BBAVF and it is unclear whether patients prefer a one-stage or two-stage procedure.[1] Currently, the decision to use one-stage or two-stage approach varies widely among access surgeons and is based on factors such as the size of basilic vein and surgeon's bias or preference. A patient-centered approach, incorporating a balance between population-based evidence and individual patient perspectives might be preferred. This pilot study will allow us to understand patient-centered outcomes and QOL measures regarding the respective BBAVF techniques. We will use the valuable results to design a Patient-Centered Outcomes Research Institute (PCORI)-sponsored pragmatic clinical trial to determine the optimal surgical procedure for a BBAVF and to understand the perspective of patients receiving a complex AVF.

The plan is to enroll 10 patients (n=5 in each group) with ESRD receiving hemodialysis with a CVC from the Banner University Medical Center. Within each cohort, the subjects will be randomized in a 1:1 ratio to one. Within each cohort, the subjects will be randomized in a 1:1 ratio to one stage and two-stage surgical approaches. The randomization scheme is as follow:

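### The only stated analysis of the primary endpoint is a log-rank test with about 10% power at five patients per arm; no effect estimate or confidence interval is specified

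*Combined protocol and SAP*

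**What the plan says.** The Statistical Analysis Plan section describes the primary analysis as a "comparison of the primary clinical functional patency by treatment approach, where the distributions are based on available follow up to 12 months", and continues: "A log-rank test will be used to evaluate the null". No estimate or interval is named for this endpoint. The one named method that would give an effect size is placed elsewhere: "The secondary analytic method of the secondary endpoints will utilize a Cox regression model". No interval is mentioned there either.

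On size, the Design section states: "The plan is to enroll 10 patients (n=5 in each group"). The Statistical Analysis Plan section takes its planning rates from a publication ("one-stage BBAVF was 56% at 12-month follow-up and was 72% for the two-stage procedure") and sizes a definitive comparison at 153 per group for 80% power, using a two-sided 5% Fisher's exact test. It then says that the pilot is exploratory and is there to show feasibility and recruitment. On later use, the Design section says: "We will use the valuable results to design a Patient-Centered Outcomes Research Institute (PCORI)-sponsored pragmatic clinical trial".

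**The concern.** The planned output does not fit the stated purpose. An exploratory pilot that feeds the design of a later trial should describe what happened in each arm and how uncertain that is. A test of the null does neither. With five patients per arm, the likely product of the plan as written is one non-significant p-value.

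The Methods section also states a directional hypothesis, that two-stage patency will be superior. A bare non-significant p-value could be taken as evidence against that hypothesis, or as evidence that the techniques are equivalent, when the data would be compatible with a large difference in either direction. The opposite error is possible too: the asymptotic log-rank test rejects somewhat more often than 5% at this size, so a significant result would also deserve little weight. Nothing in the plan says how the p-value is to be read.

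**Working it through.** **Inputs.** From the Statistical Analysis Plan section: 12-month rates of 56% (one-stage) and 72% (two-stage), two-sided 5% level, 153 per group for 80% power. From the Design section: 5 per arm, 1:1. From the Methods section: follow-up to 12 months.

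**Assumptions not in the documents.** Exponential event times, censoring at 12 months, no earlier dropout. The plan does not say whether the timed event is attaining functional use or losing patency, so both were run.

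**1. The plan's own figure.** The mean rate is 0.64.
- Uncorrected n = [1.96·√(2·0.64·0.36) + 0.8416·√(0.56·0.44 + 0.72·0.28)]² / 0.16² = (1.3305 + 0.5633)² / 0.0256 = 140.1, which rounds up to 141.
- With continuity correction: (140.1/4)·[1 + √(1 + 4/(140.1·0.16))]² = 152.3, which rounds up to 153.
- Exact Fisher power by enumeration at 153 per group is 80.3%.

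The figure of 153 is reproduced.

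**2. Power of the planned test at 5 v 5.** Simulated log-rank, 20,000 runs, two-sided 5%:

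| Event assumed | Power | Type I error |
|---|---|---|
| Loss of patency (12-month event-free 56% v 72%; null 64%) | 9.8% | 6.5% |
| Attainment of use (12-month event-free 44% v 28%; null 36%) | 9.8% | 6.1% |

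The Monte Carlo standard error of the power is √(0.098·0.902/20,000) = 0.2 points. A separate simulation of 10,000 runs gave 9.5% (loss) and 9.7% (attainment), and a type I error of about 6% to 7%. The chance of a non-significant result is therefore about 1 - 0.10 = 90%.

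**3. Cross-check by Schoenfeld's formula.** Power = Φ(|ln HR|·√(d/4) - 1.96).
- Loss: HR = ln 0.72 / ln 0.56 = 0.567. Expected events d = 10·0.36 = 3.6. Power = Φ(0.539 - 1.96) = 7.8%.
- Attainment: HR = ln 0.28 / ln 0.44 = 1.551. Expected events d = 10·0.64 = 6.4. Power = Φ(0.555 - 1.96) = 8.0%.

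**4. The sizing test at 5 v 5, for comparison only.** Fisher's test reaches p ≤ 0.05 only at 0 v 4, 0 v 5 or 1 v 5, or their reverses. Summing the binomial probabilities at 56% and 72% gives 0.0062 + 0.0032 + 0.0203 + 0.0004 + 0.0001 + 0.0012 = 0.0314, or 3.1%.

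**5. What an interval would look like.** Take 3/5 v 4/5, close to the planned rates, with complete follow-up.
- Wilson limits: 0.231 to 0.882 for 3/5, and 0.376 to 0.964 for 4/5.
- Newcombe lower limit: 0.20 - √[(0.8 - 0.376)² + (0.882 - 0.6)²] = -0.31.
- Newcombe upper limit: 0.20 + √[(0.964 - 0.8)² + (0.6 - 0.231)²] = +0.60.
- Clopper-Pearson for 3/5 alone: 15% to 95%.

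**6. Direction of the point estimate.** Enumerating the two binomials at the planned rates, one-stage leads numerically 19% of the time and the arms tie 22% of the time.

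**The case against.** The plan is candid about power. It says that 153 per group would be needed and that the pilot is exploratory. That stands: there is no false power claim here, and a reader should not infer one. But the disclosure leaves the prespecified analysis unchanged, and that analysis is still a test.

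The reference to distributions may imply Kaplan-Meier curves by arm, and the Cox sentence is loosely worded. This softens the omission. Neither commits to an estimate with an interval for the primary endpoint.

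A reader might infer that the pilot is all but certain to be non-significant, citing 3.1% power and 97%. Those figures belong to Fisher's exact test, which the plan uses only for sizing. For the log-rank test that is planned, about one pilot in ten would reject.

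A reader might also infer that the investigators intend to read non-significance as no difference. The documents do not say so. The point is that nothing guards against that reading.

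Finally, an interval spanning some 90 points will not size the next trial, for which the plan already cites external rates. That is correct. The gain is honest reporting of uncertainty, and a warning against using a 5 v 5 point estimate as a planning value. The lack of information itself comes from enrolling ten patients.

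**Conclusion.** The concern holds in a limited form. The plan names a log-rank test as the only analysis of its primary endpoint and commits to no estimate or interval. At 56% v 72% with five per arm, that test has about 10% power (about 8% by Schoenfeld's approximation) and a type I error of about 6% to 7%, so about 90% of such pilots would be non-significant if the 16-point difference is real. These figures rest on exponential times and no dropout before 12 months, and are nearly the same whichever event is timed. The defect lies in the choice and reporting of the analysis, not in the pilot's small size, which is disclosed. It should be corrected before analysis.

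**What to change.** Revise the primary analysis paragraph to say:

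- The primary result is 12-month functional patency in each randomised arm, as Kaplan-Meier estimates and their difference, each with a 95% confidence interval, alongside the raw counts. This keeps the censored comparison over available follow-up that the plan already describes.
- If every patient has complete 12-month follow-up, exact binomial intervals are used for the arms. A crude proportion should not be the default, because it leaves open how deaths and losses are counted.
- The timed event is named (attainment or loss of functional use), together with how deaths and losses enter the estimate and which interval method is used.
- The log-rank test is supportive only, and neither superiority nor absence of a difference will be concluded from its p-value.

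The cost is a short paragraph of SAP text, with no new data, patients or visits. The downside is a very wide published interval.

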**Methods:**

The target population are patients on renal replacement therapy who are receiving hemodialysis (HD) with central venous catheters (CVCs) at the time of the surgery and are candidates for a new BBAVF. The surgery is a standard of care procedure that is being done whether the potential subject is enrolled in the study. Upon enrollment the study subject will fill out the PROMIS/CAT questionnaires. The study team will follow a randomized protocol so the study subject will be randomized to the one or two stage approach. The subjects will then be seen at the standard of care intervals for follow-up. At the 6 month and 12-month standard of care follow-up visits the subjects will be asked to fill out the PROMIS/CAT questionnaires again. The subjects medical record will be followed for AE and SAE study related problems during the 12 months post surgical procedure.

Primary endpoint is Primary Clinical Functional Patency, defined as the successful use of the index fistula with two dialysis needles for at least 75% of dialysis sessions within a 4-week period to achieve the prescribed dialysis. The primary endpoint will be compared between two techniques during available follow-up up to 12-months (from the index procedure in the one-stage approach and the first procedure for the two-stage approach). Secondary endpoints will include: 1) Fistula-related outcome: stenosis and thrombosis, wound infection, arm swelling, hand ischemia, and surgery or intervention; 2) CVC-related outcome: duration of catheter-dependency, infection, bacteremia, and additional CVC procedure (exchange, placement of new catheter); and 3) Composite outcomes of Primary Clinical Functional Patency or CVC-related bacteremia or death. We will compare the PROs using the Patient-Reported Outcome Measurement Information System (PROMIS) Computerized Adaptive Testing (CAT) in the randomized patients.

Hypothesis: Primary Clinical Functional Patency will be superior following two-stage approach compared with the one-stage BBAVF approach. Patients who underwent the two-stage procedure will have higher risks of infectious complications due to a more extended CVC dependency. The PROs will be affected by the number of procedures (one vs. two), postoperative fistula-related or CVC-related complications, and the duration of CVC dependency.

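### With five patients per arm, the planned adjusted Cox models will often give no finite hazard ratio for uncommon complications modelled singly; counts with exact intervals should be the main summary.

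*Combined protocol and SAP*

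**What the plan says.** The Design section sets the size of the pilot: "The plan is to enroll 10 patients (n=5 in each group) with ESRD receiving hemodialysis with a CVC".

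The Methods section groups the secondary endpoints under three headings:
- "Fistula-related outcome: stenosis and thrombosis, wound infection, arm swelling, hand ischemia, and surgery or intervention"
- "CVC-related outcome: duration of catheter-dependency, infection, bacteremia, and additional CVC procedure"
- "Composite outcomes of Primary Clinical Functional Patency or CVC-related bacteremia or death"

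It does not say whether the items under a heading are analysed one by one or pooled. It does state a directional hypothesis about infection: "Patients who underwent the two-stage procedure will have higher risks of infectious complications due to a more extended CVC dependency".

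The Statistical Analysis Plan then gives the method: "The secondary analytic method of the secondary endpoints will utilize a Cox regression model to adjust for the subject factors", with vein size as the example of a factor to adjust for. It names no other method for the clinical secondary endpoints, no expected event rates, and no rule for endpoints with few or no events. It does call the pilot exploratory and aimed at feasibility.

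**The concern.** A Cox model estimates the treatment effect by comparing who has the event among those still at risk. If every event falls in one arm, the partial likelihood keeps rising as the log hazard ratio moves towards plus or minus infinity, so there is no finite estimate and no usable two-sided Wald interval. If neither arm has an event, there is nothing to fit. Adding vein size does not help, because the treatment coefficient can still run off to infinity. With five patients per arm and complications such as hand ischemia or bacteremia, this is an ordinary outcome.

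The pilot is meant to inform a larger trial. A hazard ratio reported as infinite or not estimable contributes little to that design, and the infection comparison that the plan itself hypothesises could be among those affected. The number of patients with the event in each arm would still be informative.

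**Working it through.** **The plan's own figure.** The only sample-size figure is 153 per group for a later full trial (two-sided Fisher's exact test, 5%, 80% power, 56% vs 72%). It reproduces: exact enumeration gives power 0.803 at 153 per group. It is not in dispute and does not bear on the pilot's Cox models, for which the plan states no figure.

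**Inputs.** n = 5 per arm (Design). Patency 56% one-stage and 72% two-stage, and 10% loss to follow-up for the full trial (Statistical Analysis Plan). All complication risks below are assumptions, because the documents give none.

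**Formula.** With 12-month risks p1 and p2 and q = 1 - p, the chance that at least one arm of five has no events is q1^5 + q2^5 - (q1·q2)^5. An empty arm is sufficient for a non-finite treatment hazard ratio, so this is a lower bound on that outcome.

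**One uncommon complication, equal risks**

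| Risk in both arms | q^5 | At least one arm empty | Neither arm has an event |
|---|---|---|---|
| 10% | 0.590 | 2(0.590) - 0.349 = 0.832 | 0.349 |
| 20% | 0.328 | 2(0.328) - 0.107 = 0.548 | 0.107 |
| 30% | 0.168 | 2(0.168) - 0.028 = 0.308 | 0.028 |

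A simulation (exponential times, censoring at 12 months, a normally distributed vein size unrelated to outcome, 8,000 replicates) finds no finite treatment hazard ratio in 84%, 56% and 33% of trials with vein size in the model. With 10% loss by 12 months this becomes 87%, 60% and 37%.

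**Infection, with the difference in the hypothesised direction**
- As one event, 10% vs 20%: 0.590 + 0.328 - 0.193 = 0.725, or 72% from the unrounded 0.7247.
- As one event, 20% vs 40%: 0.328 + 0.078 - 0.025 = 0.380.
- Three components (wound infection, catheter infection, bacteremia) pooled and treated as independent, each at 10% vs 20%: 0.9^15 + 0.8^15 - product = 0.206 + 0.035 - 0.007 = 0.234.
- The same, each at 20% vs 40%: 0.8^15 + 0.6^15 - product = 0.0352 + 0.0005 - 0.00002 = 0.036.

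Catheter infection and bacteremia overlap, so at the same component risks a pooled figure would lie between the independent-pooling value and the single-event value.

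**Composite**
- Reaching patency counted as an event (56% vs 72%): 0.44^5 + 0.28^5 - product = 0.0165 + 0.0017 - 0.00003 = 0.018.
- Patency failure counted as an event (44% vs 28%): 0.56^5 + 0.72^5 - product = 0.055 + 0.193 - 0.011 = 0.238.

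Both are upper limits on the chance of an empty arm, since adding bacteremia or death as events can only lower it. In simulation at 56% vs 72%, the hazard ratio is non-finite in about 3% of trials. Where it is finite, the median ratio of upper to lower 95% limit is about 25 unadjusted and 38 with vein size.

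**Counts.** A Clopper-Pearson interval exists for every result from 0/5 to 5/5. For 0/5 the upper limit is 1 - 0.025^(1/5) = 0.522, so the interval is 0% to 52%; for 1/5 it is 0.5% to 71.6%. These are wide but always defined.

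**The case against.** The strongest reply is that the plan may never fit the models that fail. The Methods section does not say that components are modelled singly, and the infection hypothesis speaks of complications in the plural, which can be read as a pooled outcome. Pooled, the risk of an empty arm falls sharply. This stands, and it limits the point to endpoints that remain sparse.

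A reader might infer that Cox should be dropped for every secondary endpoint. The documents do not support that: for common outcomes the hazard ratio is usually finite, and the objection there is imprecision. Nor do they show that the composite is safe. The 1.8% figure holds only if reaching patency is the event, and the wording leaves that open.

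A penalised (Firth) Cox model would give finite estimates when only one arm has events. The plan does not name it, and it cannot help when neither arm has an event (35% of trials at 10% risk, 11% at 20%). It is also fair to say that a non-finite fit would be visible, that a one-sided bound can still be obtained, and that nothing in the plan forbids reporting counts. A claim that the method yields no information would therefore go too far.

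A further objection is that exact proportions ignore incomplete follow-up, which the plan foresees for the primary endpoint: "The primary endpoint will be compared between two techniques during available follow-up up to 12-months". At 10% loss, all ten patients are followed with probability 0.9^10 = 35%. That is a real limitation. Kaplan-Meier does not escape the sparse-data problem, though: with no events its estimate is 0 and its usual variance is 0, so its interval is degenerate.

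**Conclusion.** The concern holds for uncommon secondary endpoints modelled separately. At assumed risks of up to about 20% per arm, more than half of such models would give no finite treatment hazard ratio; at 30%, about a third would. For infection the size depends on how it is defined: 72% or 38% as one event, about 23% or 4% pooled. For the composite it is at most 1.8% or up to 24%, depending on which direction of patency is the event. All complication rates are assumed, and the pooled figures also assume independence.

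A reader might take this as a criticism of the sample size. It is not: the plan discloses what a powered trial would need and labels the pilot exploratory. Nor does it concern the primary endpoint, for which the plan names a log-rank test; how that result is reported is a separate matter. The change is worth making because the prescribed method can fail for a comparison that the plan itself hypothesises, and a summary that cannot fail is available at little cost.

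**What to change.** In the Statistical Analysis Plan:
- State that the main summary of each event-type secondary endpoint is the number of patients with the event by randomised arm, out of all randomised, with a Clopper-Pearson 95% interval. List deaths and losses before 12 months beside it.
- Report catheter-dependency duration descriptively by arm, with the reason it ended for each patient.
- Fit a Cox model only as a supplementary analysis, labelled exploratory, where both arms have events. Do not use it for an endpoint with an empty arm.
- Show vein size by arm as a baseline description.

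The cost is wording only: no new data, no change of endpoint and no change of sample size. There are two downsides. Sparse endpoints will have no covariate-adjusted hazard ratio. With incomplete follow-up, the observed proportion may understate the 12-month risk, which the listed deaths and losses make visible.

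### Does inflating 153 to 168 per arm for 10% loss, where dividing by 0.90 gives 170, leave the plan short of its stated 80% power?

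*Combined protocol and SAP*

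**What the plan says.** The sample-size text is in the Statistical Analysis Plan section. It takes 12-month functional patency of 56% for the one-stage and 72% for the two-stage procedure. It names the test and level ("Based on a two-sided Fisher's exact test at significance level of 5" per cent) and states that "a sample size of 153 per group is required to achieve a power of 80" per cent. The next sentence gives the enrolled size: "A sample size of 336 participants (168 per arm), with an estimated loss to follow-up rate of 10" per cent. It shows no inflation formula, and it describes 336 as what is needed for the 5% significance level rather than for the power.

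Two other statements bear on the point. For the primary endpoint the same section says that "A log-rank test will be used to evaluate the null", and that "the distributions are based on available follow up to 12 months". The Design section sets enrolment at 10 patients, 5 per group. The Statistical Analysis Plan section calls the pilot exploratory, limited by the grant's time and resources.

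**The concern.** Two adjacent sentences do not agree. If 153 evaluable patients per group are needed and 10% of those enrolled are lost, 168 per arm is not enough to leave 153. Adding 10% to the evaluable number, instead of dividing by 0.90, is a familiar mistake and always gives too small a figure. The wording about the significance level adds to the impression of carelessness, because that level is fixed in advance and sample size determines power.

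The Design section says the pilot's results will be used to design a later pragmatic trial, and 336 is the only full-trial size in the document. If it were copied forward, that trial might start slightly below its intended power.

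**Working it through.** **Inputs, all from the Statistical Analysis Plan section except allocation.** p1 = 0.56, p2 = 0.72, two-sided α = 0.05, power 80%, Fisher's exact test, loss 10%. Allocation is 1:1 (Design section).

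**Step 1: reproduce 153.** With pooled proportion 0.64, the uncorrected normal formula is

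n = [1.960·√(2·0.64·0.36) + 0.842·√(0.56·0.44 + 0.72·0.28)]² / 0.16² = 140.1, that is 141.

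The continuity correction gives

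n′ = (140.1/4)·[1 + √(1 + 4/(140.1·0.16))]² = 152.3, that is 153.

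This matches the plan. Full enumeration of the two-sided Fisher test gives 80.1% power at 152 per group and 80.3% at 153. So 153 is sound, and very slightly more than the minimum.

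**Step 2: reproduce 168.**

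- 153 × 1.10 = 168.3, which rounds to 168; 2 × 168 = 336. This matches the plan.
- 153 / 0.90 = 170; 2 × 170 = 340. This does not match.

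Use of the factor 1.10 is an inference, since no formula is given, but it fits and division by 0.90 does not.

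**Step 3: the shortfall.** 168 × 0.90 = 151.2 remain, against 153. The enrolled size is short by 170 − 168 = 2 per arm, or 4 in total (4/336 = 1.2%).

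**Step 4: what it does to power.** Exact two-sided Fisher power for 56% vs 72%, by enumeration:

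| Evaluable, one-stage / two-stage | Power |
|---|---|
| 151 / 151 | 79.7% |
| 152 / 152 | 80.1% |
| 153 / 153 | 80.3% |
| 151 / 152 | 81.9% |
| 152 / 151 | 81.1% |
| 150 / 152 | 80.5% |

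Fisher's test is discrete, and in these cases it is more conservative when the arms are exactly equal. The 79.7% is therefore a special case: moving one patient to 151/152 lifts power by about 2 points.

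**Step 5: average over random loss.** Assume each patient is lost independently with probability 0.10. The evaluable number in each arm is then binomial with retention 0.90. Weighting the exact power of each pair of arm sizes by its probability gives:

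- 168 per arm: mean power about 81.2%
- 170 per arm: mean power about 81.8% (a coarser check with 250 simulated draws gave 81.7%)

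The difference is about half a percentage point, and both means exceed 80%.

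**The case for a change.** The best case for a change is that the plan contradicts itself, whatever the consequence. It states a requirement of 153 and then an enrolment that, with its own loss rate, leaves 151.2. At exactly 151 per arm the power is below 80% on the plan's own test, and at 152 it is not, so the slip sits on the wrong side of the line. The wording about the significance level is wrong at any sample size. Correcting both takes one sentence, and the figure could be copied into the later application.

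The arithmetic part of this stands: 170 and 340 are the conventional figures, and anyone sizing the later trial should use that method. The point about wording also stands, but it misleads nobody, because the sentence before it gives the 80% power and the 5% level correctly.

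The claim of lost power does not stand. It depends on both arms ending at exactly 151. It also treats every lost patient as contributing nothing, whereas the planned log-rank comparison uses follow-up up to the point of loss. The effective loss of information is therefore probably below 10%.

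The risk of copying is weak as well. The protocol does not fix the later trial at 336; it says that trial will be designed from the pilot's results.

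**Conclusion.** This is a clerical slip with no consequence for the study. The inflated size is 2 per arm (4 in total, 1.2%) below what division by 0.90 gives. Mean Fisher power from 168 per arm is still about 81.2%, roughly half a point below that from 170. That result rests on the plan's own rates, test and level, and on the assumption that losses are independent and equally likely in both arms.

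The figure governs nothing in the 10-patient pilot, where it only explains why a powered comparison is not attempted. Changing 336 to 340 would not alter enrolment, analysis or interpretation. No change to the plan is needed.

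### PROMIS change scores are compared between arms with no baseline covariate; adjusting for the collected baseline score removes chance imbalance in expectation, at a precision cost that depends on the correlation

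*Combined protocol and SAP*

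**What the plan says.** The Statistical Analysis Plan defines the arm comparison of patient-reported outcomes in one sentence: changes in individuals' "PROMIS domain scores and overall scores from the baseline will be compared between the patients" treated in one stage and those treated in two stages. It names no model, covariate, test or primary time point for that comparison.

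The only test in the paragraph belongs to another question, the impact of clinical events "on PROMIS domain scores will be evaluated using the student T-test". The only baseline adjustment in the plan is a Cox regression for the secondary endpoints, with vein size as the example. That model is for times to event and cannot serve a continuous score.

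The baseline score is available. Methods states "Upon enrollment the study subject will fill out the PROMIS/CAT questionnaires" and then "At the 6 month and 12-month standard of care follow-up visits the subjects will be asked to fill out the PROMIS/CAT questionnaires again". The Design section enrolls 10 patients, five per group, and "the subjects will be randomized in a 1:1 ratio to one stage and two-stage surgical approaches". The PROMIS paragraph also narrows the set analysed: "The analysis will be performed after excluding those who do not complete the two-stage procedure".

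**The concern.** A change score subtracts the whole baseline value, although follow-up depends on baseline only with slope rho when the SD is the same at both times. It therefore over-corrects. The arm that happens to start lower will, through regression to the mean, tend to show the larger improvement with no treatment effect at all.

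With five patients per arm, sizeable chance differences at baseline are to be expected, and a reader of this one trial must interpret the imbalance actually drawn. The plan accepts elsewhere that baseline imbalance may need adjustment, but provides none for PROMIS. These outcomes are prominent in the rationale: the Design section says the pilot is meant to inform understanding of patient-centered outcomes and quality of life under the two techniques.

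**Working it through.** **The plan's own figure.** No figure is stated for PROMIS. The only sample-size figure, 153 per group for patency of 56% v 72% (two-sided 5%, 80% power), reproduces. The uncorrected two-proportion formula gives 141, the continuity-corrected one gives 153, and exact enumeration of Fisher's test gives 80.3% power at 153. It is used below only as the scale of a large trial.

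**Inputs.** From the documents: 5 per arm (Design); PROMIS at enrollment, 6 and 12 months (Methods); exclusion of two-stage non-completers (Statistical Analysis Plan). Assumed, because the documents give none: normal scores, SD 10 at each time, rho from 0.3 to 0.9.

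**1. Size of the chance imbalance.** SD of the baseline difference = 10 x sqrt(1/5 + 1/5) = 6.3 points. It exceeds 5 points in either direction in about 43% of randomisations.

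**2. What the change contrast carries.** Given a baseline difference d, the expected change contrast is the treatment effect plus (rho - 1) x d. For d = 5 the shift is 5 x (1 - rho), in the opposite direction to d. In simulation (100,000 trials per setting), the change contrast correlated with d at -0.59 (rho 0.3) to -0.22 (rho 0.9), and the ANCOVA contrast at about 0. Over all randomisations both contrasts were unbiased, with type I error near 5%.

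**3. What adjustment costs.** With n1 and n2 analysed and N = n1 + n2:

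- Var(change) = 2 x SD² x (1 - rho) x (1/n1 + 1/n2)
- Var(ANCOVA) = SD² x (1 - rho²) x (1/n1 + 1/n2) x (1 + 1/(N - 4))

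The last factor is the price of estimating the slope. At 5 v 5 it is 1 + 1/6 = 1.167. Residual degrees of freedom fall from 8 to 7, and the t critical value rises from 2.306 to 2.365. The variance ratio ANCOVA/change is (1 + rho)/2 x 7/6.

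| rho | Shift for d = 5 (points) | Variance ratio | Simulated CI-width ratio | Power for 10 points, change v ANCOVA |
|---|---|---|---|---|
| 0.3 | 3.5 | 0.76 | 0.88 | 22% v 27% |
| 0.5 | 2.5 | 0.88 | 0.95 | 28% v 32% |
| 0.6 | 2.0 | 0.93 | 0.98 | 34% v 36% |
| 0.7 | 1.5 | 0.99 | 1.01 | 43% v 43% |
| 0.8 | 1.0 | 1.05 | 1.04 | 59% v 57% |
| 0.9 | 0.5 | 1.11 | 1.07 | 87% v 82% |

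**4. Break-even at 5 v 5.** On variance: rho = 2/(7/6) - 1 = 0.71. Counting the lost degree of freedom, on approximate squared CI width: rho = 1.714/(2.365/2.306)² - 1 = 0.63.

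**5. After the planned exclusion.** If two two-stage patients drop out of the set (5 v 3), the factor is 1 + 1/4 = 1.25 and degrees of freedom fall from 6 to 5 (t from 2.447 to 2.571). Break-even is 2/1.25 - 1 = 0.60 on variance and 1.6/(2.571/2.447)² - 1 = 0.45 on squared CI width. At rho 0.8, power for 10 points is 44% for change and 40% for ANCOVA.

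**6. Large trial.** At 153 per group the factor is 1 + 1/302 = 1.003, and the variance ratio runs from 0.65 (rho 0.3) to 0.95 (rho 0.9).

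**The case against.** The strongest objection is that at ten patients the choice hardly matters. At rho 0.5 the mean CI half-width is 14.1 points for change and 13.4 for ANCOVA; neither is informative. The plan calls the pilot exploratory and aims it at feasibility. The slope is itself poorly estimated (standard error about 0.35 around a true 0.5), so the correction is right in expectation but noisy in any one trial. If rho is high, or exclusions shrink the two-stage arm, ANCOVA is the less precise method. All of this stands and limits the weight of the point. It does not remove it, because the change contrast still depends on the baseline difference drawn, and the covariate is already collected.

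It can also be said that "unadjusted" is read from silence, since no method is named for the arm contrast. That is fair. But nothing in the text supports an adjusted reading, and the silence itself needs filling.

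A reader might go further in three ways that the documents do not support:

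- That adjustment is almost free even at five per arm. It is nearly free at 153 per group; at 5 v 5 the slope adds about 17% to the variance and uses one of 8 degrees of freedom.
- That the change contrast is biased. It is not, on average; the shift is conditional on the allocation drawn.
- That this pilot's PROMIS effect and SD estimates will be carried into the planned PCORI trial. The Design section says only that the results will be used to design it, and the one sample-size calculation rests on published patency rates.

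**Conclusion.** The point holds as a cheap improvement, not as a flaw that invalidates the pilot. The planned PROMIS contrast uses change from baseline without the baseline score as covariate, so a 5-point chance imbalance moves it by 0.5 points (rho 0.9) to 3.5 points (rho 0.3). Baseline adjustment removes that dependence in expectation.

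The net effect on precision at 5 v 5 runs from an interval about 12% narrower (rho 0.3) to 7% wider (rho 0.9), with break-even near 0.63 to 0.71. At 5 v 3 break-even falls to about 0.45 to 0.60. Since neither SD nor rho is given, the direction of the net effect in this pilot is unknown. The shift in points scales with the assumed imbalance, and the SD of that imbalance scales with the assumed SD; the ratios do not depend on the SD but do rest on normal scores with equal SD at both times.

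One limit applies whatever rho is. Because two-stage non-completers are excluded, imbalance in the analysed set need not be due to chance alone, and a baseline covariate does not repair that selection.

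**What to change.** Add to the Statistical Analysis Plan that each PROMIS domain score and the overall score at 6 and 12 months will be compared between arms by ANCOVA, with the baseline value of the same score as covariate, reporting the adjusted difference and its 95% CI. Keep mean change per arm as a descriptive summary. If change is preferred as the outcome, adding the baseline covariate gives the same arm estimate. State beside it that, at this sample size, the adjusted interval may be somewhat wider than the unadjusted one if the correlation is high.

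The cost is a sentence or two and no new data, plus the degree of freedom and slope-estimation cost shown above. The sentence should not be allowed to change the analysis set by implication; whether two-stage non-completers stay excluded is a separate decision to be stated in its own right.
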